## **Study Aims**

Aim 1. To assess the subjective and clinical effects of NR on ENDS users. Participants will undergo 2 ENDS use sessions that are preceded by 12-hour abstinence, with session order counter-balanced to mitigate order and carry-over effects. This study will focus on pre-post-use assessment of craving, withdrawal, satisfaction, intention to quit or use in the future, lung functions (e.g. FEV1 % predicted; FEV1/FVC, CO diffusing capacity-DLCO), and symptoms (e.g. dry mouth, eye irritation, palpitation, nausea). This aim will show ENDS users' response to NR on product satisfaction, dependence, lung functions and symptoms.

Aim 2. To assess puffing behavior in response to NR. Under the same protocol, puff topography (e.g. puff volume, puff frequency, duration) will be assessed continuously during the 2 sessions, while plasma nicotine will be measured pre-post sessions to assess nicotine boost and its correlation to puffing parameters. This aim will help understand users' compensatory puffing in response to NR and its effect on plasma nicotine.

Aim 3. To assess exposure to toxicants associated with NR. We will measure toxicant emissions (14 aldehydes) in the analytical lab using a smoking robot that reproduces the puff-by-puff behavior (playback) of each participant for all two nicotine conditions (Aims 1, 2). This aim will reveal how compensatory puffing behavior in response to NR influences acute exposure to pulmonary toxicants.

The proposed studies will give clear evidence on the potential of NR regulations to limit the addictiveness and use of ENDS, and to help predict any potential side effects of NR on ENDS users.

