## **Study Design**

This study is divided into 2 parts (studies), whereby the first part will be 2X2 comparing NJOY 5% and 3% to test the effects of partial nicotine reduction, and the second part will be using the NIDA Standardized Research Electronic Cigarette (SREC) for Clinical Research 5% and 0% (placebo), to test the effect of the total reduction using the same pods and juices from the same manufacturer.

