Screening, and informed consent: Individuals who are identified as potentially eligible based on the phone screening will be asked to attend an onsite-screening, which will involve assessment of inclusion/exclusion criteria, physical examination, COVID-19 screening, and urine pregnancy testing for women. Prior to screening, potential participants will undergo a review of the study and consent procedures to ensure that they understand the study, its risks/benefits, and their rights as research participants. Consented (written) individuals will then undergo a physical examination conducted by the research nurse, who will have access to an on-call Medical Monitor (physician) in case of concern or for consultation at any point of the study as it is the standard practice in our lab. Successfully consented participants will be scheduled for their 1st session and asked to abstain from all tobacco/nicotine use 12 hours prior to it.

Sample size. All power calculations were performed with PASS19 (PASS, 2019). We built our calculation of the sample size for this study based on our preliminary study of the effect of NR on subjective (e.g. craving, urges) and puff topography measures (pls. see Preliminary Studies), where medium effect size (Cohen's  $f=0.2$ ) depending on nicotine condition was detected. Expecting a maximum 20% loss due to noncompliance with abstinence or study protocol (Vargas-Rivera et al., 2020), this study will include a dropout inflated sample of 150 ENDS users. Using repeated measures ANOVA F-test with 2 within and 1 between factors, a total dropout adjusted sample size of 120 (2X60) participants will have at least 80% power to detect small to medium-size effect (Cohen's  $f=0.1-0.2$ ) or larger for 2 within-subject (NR condition and time) and 1 between subject (use frequency) factors, as well as their interactions at 0.05 level of significance, assuming sphericity and a moderate correlation (0.5) among repeated measures (Cohen, 1988).

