## **AIM 3: To assess exposure to toxicants associated with nicotine reduction.**

**Objective and hypothesis:** This aim will help elucidate how compensatory puffing behavior in response to NR affects exposure to pulmonary toxicants. *We hypothesize that partial but not total NR will be associated with compensatory puffing behavior that will, in turn, lead to greater exposure to toxicants.*

**Analytical methods.** The analytical assessments will be conducted at the AUB Aerosol Research Laboratory (ARL). The ARL is equipped with two digital playback smoking machines necessary for Aim 3. These two machines, developed and tested by our team at AUB, are to our knowledge unique to this setting and are not available in any other laboratory. The proposed work in Aim 3 is built on the ARL framework and infrastructure for aerosol generation, sampling, and chemical analysis.

**Aerosol generation and sampling:** The deidentified puff topography data will be shared via Microsoft Sharepoint between FIU and AUB Aerosol Lab, thus, all communication will be encrypted between client and server using SSL 2048 bit keys. Access to the lab and data will be granted only by permission of Drs. [name] (PI), and [name] (local PI at AUB).

Once the puff topography files have been received by the ARL, we will use ALVIN (Aerosol Lab Vaping Instrument) (Talih et al., 2015, 2017) to draw aerosols from the ENDS devices, for each of the 240 topography sessions. For each session, ALVIN will be programmed to reproduce the puff topography data generated in the clinical lab. The generated aerosol will be drawn through a Gelman type A/E 47mm glass fiber filter followed by a 2,4-dinitrophenylhydrazine-coated silica cartridge (type LpDNPH H10) cartridge, for nicotine and aldehydes quantification, respectively (see Talih et al., 2015, 2017; El-Hellani et al., 2018 for more detail). The pods (e.g. JUUL) and batteries will be shipped from the same batch as those used at FIU to minimize biases. A new pod will be used for every session. Each pod will be pre-conditioned before sampling by drawing 15 4-second puffs at 1 LPM using ALVIN. We will use a quality assurance protocol and ENDS electrical performance tester developed at the ARL to ensure that each battery and pod are within tolerance (Talih et al., 2019, 2020b).

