## Statistical analysis

Topography data will be processed automatically by the topography instrument software (Spindle et al., 2015, 2017) to eliminate closely spaced puffs (i.e., IPIs < 300 msec). Such puffs are assumed to be part of the previous puff and the recorded volume and duration values will be added to that preceding puff. After this procedure, any puffs less than 5 ml will be considered an artifact and automatically discarded. The remaining data will be averaged for each participant in each condition using all remaining values for puff volume, duration, number, and IPI (Robinson et al., 2018). For plasma nicotine, values below the limit of quantitation (LOQ) will be replaced with the value of the LOQ, 2 ng/mL (Spindle et al., 2017).

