mentioned covariates. Given the known sex-related differences in nicotine dependence (Benowitz et al., 2006), to assess if sex has any effect on the results, it will be considered as a covariate and we will test the pre-planned interaction with it to determine the heterogeneity of the study outcomes by sex as well as potential differential effects. Similarly, for categorical outcomes we will apply generalized linear models and estimating equations with the same main effects as described above, modeling within factors as random effects. We will test for the carry-over effect statistically and will control for it when testing for the primary factors (Senn, 2002).

For Aim 3, we will use a one-way ANOVA to test the effect of NR on aldehyde emissions and multiple linear regression analysis to assess the influence of puff topography data (puff volume, duration, number, and interpuff interval) on aldehyde emissions. Additionally, we will measure the relation between the plasma nicotine levels obtained in the clinical lab and measured nicotine yields obtained in the analytical lab using linear regression. Significance levels will be adjusted for violations of the sphericity assumption using Huynh-Feldt corrections (Keppel, 1991). All differences will be considered significant at the alpha level of 0.05 using adjusted p-values where appropriate. Due to the nature of laboratory data collection, missing data is rare and it usually occurs due to instrument malfunction. All data are collected and checked for completeness by laboratory staff. In the case of missing data, which we expect to be minimal, we will use a regression model based on multiple imputations with all available outcome data, demographic, and clinical variables as predictors. This will be carried out in 25 random repetitions under missing at random assumption, analyzed using methods described above and results will be combined to produce unbiased overall estimates and standard errors of the experimental conditions. As a sensitivity analysis completers results will be compared with multiple imputation results.

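### The plasma-on-yield regression does not separate the nicotine-free sessions, so it can show a yield-uptake relation that is absent among nicotine sessions (minor; cheap to fix)

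*Combined protocol and SAP*

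**What the plan says.** The Aim 3 paragraph of Statistical analysis adds one sentence on this regression. Its subject is "the relation between the plasma nicotine levels obtained in the clinical lab and measured nicotine yields obtained in the analytical lab using linear regression". Nothing further is said about the model.

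Other sections bear on what enters it:

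- Study Design: the second part compares two versions of the NIDA "Standardized Research Electronic Cigarette (SREC) for Clinical Research 5% and 0% (placebo"), so one of each participant's two sessions there is nicotine-free.
- AIM 3: playback yields are produced "for each of the 240 topography sessions", with no exception for 0% sessions.
- Study Aims, Aim 2: "plasma nicotine will be measured pre-post sessions to assess nicotine boost and its correlation to puffing parameters". Boost is therefore available, but it is named for puffing and not for yield.
- Statistical analysis: plasma values below the limit of quantitation "will be replaced with the value of the LOQ, 2 ng/mL".
- Participants and recruitment: abstinence is confirmed by pre-session plasma nicotine below 5 ng/ml, and data from non-compliant participants are to be removed.

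**The concern.** This is the only stated analysis that ties machine-measured nicotine yield to nicotine measured in participants. Its use is to show whether a higher played-back yield goes with higher uptake.

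A 0% session contributes a yield of about zero and a plasma value near the 2 ng/mL floor. Nicotine sessions have positive yield and, on average, higher plasma. A straight line through both groups must slope upwards because nicotine raises plasma and its absence does not. That is known beforehand and says nothing about whether yield tracks uptake from one nicotine session to another. A reader shown a small p-value and a moderate R-squared could take the playback yields as validated when that had not been tested.

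**Working it through.** **Sessions.** 120 participants × 2 sessions = 240, which reproduces the plan's figure. The sample size text gives "a total dropout adjusted sample size of 120 (2X60) participants will have at least 80% power" but no split between the two parts. I assume 60 per part, so 60 of 240 sessions are nicotine-free (share p = 0.25). In the second part alone the share is 60 of 120 (p = 0.50).

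**Weight of the nicotine v none contrast.** Let c be the coefficient of variation (CV) of yield among nicotine sessions. With zero yield at 0%, the share of yield variance due to nicotine v none, which is also its weight in the all-session slope, is p/(p + c²):

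| c | all 240 sessions | second part alone |
|---|---|---|
| 0.3 | 74% | 85% |
| 0.5 | 50% | 67% |
| 0.7 | 34% | 51% |
| 1.0 | 20% | 33% |

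The share passes one half when c < √p, that is, below 0.50 (all sessions) or 0.71 (second part).

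**R-squared with no relation among nicotine sessions.** Assumptions, none from the documents: yield and plasma lognormal with log SD 0.5; mean plasma 8 ng/mL; 3% sessions distributed like 5% sessions; 0% plasma fixed at 2. Then c² = exp(0.25) − 1 = 0.284. The plasma variance among nicotine sessions is 64 × 0.284 = 18.2, and the gap in mean plasma is 8 − 2 = 6. In large samples

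R² = [p/(p + c²)] × [p/(p + 18.2/36)].

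- Second part: (0.50/0.784) × (0.50/1.005) = 0.638 × 0.498 = 0.32.
- All sessions: (0.25/0.534) × (0.25/0.755) = 0.468 × 0.331 = 0.155.

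Simulation at the actual numbers of sessions (2,000 runs) gives 0.34 and 0.16, against about 0.01 to 0.02 within nicotine sessions. The slope had p < 0.05 in 100% of runs in both cases.

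**0% plasma spread evenly over 2 to 5 ng/mL.** The mean gap becomes 8 − 3.5 = 4.5 and the variance within the 0% group is 3²/12 = 0.75. The second factor becomes p(1−p)4.5² / [p(1−p)4.5² + (1−p)18.2 + 0.75p].

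- Second part: 5.06/(5.06 + 9.09 + 0.38) = 0.349; × 0.638 = 0.22.
- All sessions: 3.80/(3.80 + 13.63 + 0.19) = 0.216; × 0.468 = 0.10.

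Simulation gives about 0.24 and 0.11.

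**Other spreads (simulation, 0% plasma fixed at 2).** At log SD 0.3, R-squared is 0.64 (second part) and 0.44 (all sessions). At log SD 0.8 it is about 0.12 and 0.04, with p < 0.05 in about 95% and 79% of runs. Letting 0% plasma vary lowers these.

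**Pre-session nicotine.** Held between 2 and 5 ng/mL, it has SD 3/√12 = 0.87 if uniform and at most 1.5. If independent of yield it leaves the slope unchanged. In all-session fits it lowers R-squared by at most 0.03 at mean boost 10 ng/mL (0.07 in the extreme case of half at 2 and half at 5), and by up to 0.09 at mean boost 5. With c = 0.5 and mean boost 10, replacing level by boost while keeping the 0% sessions moves R-squared only from 0.43 to 0.44, 0.59 to 0.60 or 0.77 to 0.79. The within-nicotine values in those three cases are 0.10, 0.30 and 0.60.

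**The case against.** The strongest reply is that the sentence is brief, not wrong. It introduces a supporting analysis that tests no stated hypothesis and enters no sample size. The investigators could well use boost and analyse the parts separately. Much of this stands, and it limits the point in four ways.

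- A reader might infer that the plan chose the wrong variable. It did not: the word levels leaves pre-use, post-use and change all open, and both samples are scheduled.
- A reader might infer that both parts are pooled. The text is silent, and the primary analysis lists the two concentration pairs as alternatives. Analysis by part would clear the first part (5% v 3%), but half of the second part's sessions would still be nicotine-free, and there the effect is larger.
- A reader might infer that slope and R-squared mainly reflect nicotine v none. That requires a yield CV below 0.50 or 0.71, and the documents give none.
- A reader might count pre-session nicotine as an equal cause. The 5 ng/ml criterion and the 2 ng/mL substitution confine it. It would bias the slope only if correlated with yield, for example through use frequency, which the documents do not quantify.

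What the reply does not remove is that the model as stated, applied to the sessions as stated, includes the 0% sessions and has no term that separates them.

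**Conclusion.** The concern holds as a minor improvement to a secondary Aim 3 analysis. Followed as written, the regression can report a significant yield-uptake relation when none exists among nicotine sessions. Under log SD 0.5 and mean plasma 8 ng/mL, the spurious R-squared is about 0.24 to 0.34 in the second part alone and 0.11 to 0.16 over all sessions. Each range runs from 0% plasma spread over 2 to 5 ng/mL to 0% plasma fixed at 2. The values shrink to about 0.12 and 0.04 at log SD 0.8 (0% plasma fixed at 2). All of them rest on assumed spreads, 60 participants per part, and 3% sessions distributed like 5% sessions. The documents do not support saying that the result would be mostly artefact, or that using levels is itself the main fault. Separating the 0% sessions matters far more than the switch to boost.

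**What to change.** Replace the sentence in Statistical analysis with a specified model:

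- **Outcome:** post-use plasma nicotine with pre-use plasma as covariate, or the boost (post minus pre).
- **Terms:** yield, product and concentration (NJOY 5%, NJOY 3%, SREC 5%), and a participant random effect for the two sessions.
- **Main slope:** nicotine-containing sessions only, 240 − 60 = 180 assuming 60 per part. Participants in the first part supply two sessions each (120) and those in the second part one each (60).
- **Separate report:** the 0% sessions as a check that yield and boost are near zero, or the all-session fit labelled as including the nicotine v none contrast.

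The cost is a few lines of SAP text, since both plasma samples and all yields are already planned. The downside is fewer sessions and a narrower yield range, so the slope will be less precise. The sample size is unaffected.

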### **Protection of human subjects**

This project involves three Aims: 1) analyzing the subjective effects of nicotine reduction on ENDS users; 2) evaluating the compensatory puffing behavior in responses to nicotine reduction; and 3) assessing toxicant exposure associated with nicotine reduction in ENDS users. All three Aims involve human research subjects that will participate in a crossover lab study that will take place at [name]'s Clinical Research Lab for Tobacco Smoking at Florida International University (FIU; <https://stempel.fiu.edu/clinical-research-lab-tobacco-smoking>). Prior to initiating the study, the project principal investigator at the study site ([name]; FIU) will submit and obtain IRB approval. In addition, all IRBs in participating institutions require that all key personnel of studies involving human subjects undergo training on human research subjects' safety (e.g., <http://research.fiu.edu/irb/>) and receive a certificate from the Collaborative IRB Training Initiative Program (CITI; <https://www.citiprogram.org/>) prior to any study (part of the IRB approval). A study guide will be developed for the lab study, and the procedures will be followed. All study personnel will be trained in all study procedures, including recruitment, informed consent, and data collection methods. Adherence to the procedures in the study guide will be assured by periodic assessment and retraining. Prior to any data collection, participants will provide written IRB-approved consents that explain the study objectives, procedures, risk and benefits, measures to protect the confidentiality, and voluntary participation/withdrawal from the study at any time. Should changes to the study protocol become necessary, protocol amendments will be submitted to the IRB for approval before implementation. All recruitment materials will be IRB approved.
